**Laboratory Test Abnormalities due to Test Value Decrease**

Test	Abnormality	Test Result Grade				
		-4	-3	-2	-1	0
Glucose (mg/dL)	Decrease	< 30	30 - < 40	40 - < 55	55 - < 65	≥ 65
Hemoglobin (g/dL)	Decrease	< 6.5	6.5 - < 8	8 - < 10	10 - < LLN	LLN
Lymphocytes, Absolute (Thous/ $\mu$ L)	Decrease	< 0.2	0.2 - < 0.5	0.5 - < 0.8	0.8 - < LLN	LLN
Neutrophils, Absolute (Thous/ $\mu$ L)	Decrease	< 0.5	0.5 - < 1	1 - < 1.5	1.5 - < LLN	LLN
Platelet Count (Thous/ $\mu$ L)	Decrease	< 25	25 - < 50	50 - < 75	75 - < LLN	LLN
Potassium (mEq/L)	Decrease	< 2.5	2.5 - < 3	-	3 - < LLN	LLN
Sodium (mg/dL)	Decrease	< 120	120 - 124	125 - 129	130 - 135	≥ 136
White Blood Count (Thous/ $\mu$ L)	Decrease	< 1	1 - < 1.5	1.5 - < 2.5	2.5 - < 3.501	≥ 3.501

**Appendix 2                      Criteria of Potentially Clinically Significant Vital  
Sign Abnormalities**

Test Type	Test Parameters	Unit	Sex	Criteria (meet either one will count)	
				Limit	Change from baseline
VITAL SIGNS	SBP, SITTING	mmHg	Male/Female	$\geq 180$	$\geq 20$
VITAL SIGNS	SBP, SITTING	mmHg	Male/Female	$\leq 90$	$\leq -20$
VITAL SIGNS	DBP, SITTING	mmHg	Male/Female	$\geq 105$	$\geq 15$
VITAL SIGNS	DBP, SITTING	mmHg	Male/Female	$\leq 50$	$\leq -15$
VITAL SIGNS	HEART RATE	bpm	Male/Female	$\geq 120$	$\geq 15$
VITAL SIGNS	HEART RATE	bpm	Male/Female	$\leq 50$	$\leq -15$
VITAL SIGNS	TEMPERATURE	degree C	Male/Female	$\geq 38.3$	$\geq 1.1$
VITAL SIGNS	WEIGHT	kg	Male/Female	-	$\geq 7$ percent

## 210 ANOVA Table of Change from Baseline on eGFR Follow-up Observations

## Post Treatment Follow-up Visits 1, 2, and 3

Source	DF	SS	MS	F-value	P-value
Between	9	1709.75	189.97	14.81	<.0001
Within	15	192.36	12.82		
Corrected Total	24	1902.10			

Because the mean sum square of within-subject error (12.82) in study 210 is only ~6.7% of the mean sum square of between-subject error (189.97), we may conclude that the increase of eGFR observations (use of more than one observation) does not reduce the variance of their average much, since increased numbers of observations only reduce the within-variance component in their average, and there is little within-subject variation to be further reduced.

Since the 210 eGFR data used for this blinded sample size re-calculation are based on Rate Blank serum creatinine, this fact may raise the question of whether the within-subject errors of these two kinds of serum creatinine are very different or not. It is likely that Rate Blank serum creatinine is more stable with less within-subject variation. Indeed, this was considered an advantage of the Rate Blank method when our central lab vendor, Covance, recommended it to us. Thus, it is not known whether the small within-subject error in 210 is caused by Rate Blank data or is actually occurring in 210 eGFR data. Because of this, there are no grounds for making any changes to the number of eGFR observation at pre-treatment baseline and post-treatment follow-up visits, unless 210 eGFR data based on Enzymatic serum creatinine are available. Based on the current clinical operation plan, Enzymatic serum creatinine data are only available when subjects finish their 12-month visits as well as their post-treatment follow-up visits (for both completer and early withdrew subject), since batched analysis on frozen blood samples of all visits would only be done after that. Thus, more appropriate analysis to determine the number of eGFR observations at pre-treatment baseline and post-treatment follow-up visits can only be provided after more subjects complete the study.

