
Criteria for Evaluation:
	
Primary Efficacy Endpoint: Treatment difference in the change of eGFR from pre-treatment baseline to post-treatment follow-up, annualized (divided) by each subject's IMP treatment duration.
 
Secondary Endpoints: Key Secondary Efficacy Endpoint: Treatment difference in annualized slope of eGFR calculated for individual subjects using an appropriate baseline and available post-randomization, on-treatment assessments.
 
Safety Endpoints:
 
1) AEs2) Vital signs3) Clinical laboratory tests, including serum transaminases, total bilirubin (BT), alkaline phosphatase (ALP), and serum sodium. 
PK Endpoints: Plasma tolvaptan and metabolite(s), including DM-4103 plasma concentrations.
 
PD Endpoints: Uosm and urine specific gravity.
 
Exploratory Endpoints: [REDACTED]

---------------------------------	---

Statistical Methods:

Sample size: Based on a Mixed Model Repeated Measurements analysis of the [REDACTED] CKD-3 subjects from trial [REDACTED], the treatment difference in renal function at Month 12 is 1.07 in our sample size calculation. It is expected that the intra-subject variance is 14.2 and inter-subject variance is 28.05 at Month 12. With 3 repeated measures at pre-treatment baseline and post-treatment follow-up, respectively, the power calculation estimates that, for a 2-sided alpha set at 0.05 for a power of 90%, and with an assumption of 10% dropout rate in the trial, a total sample size of approximately 1300 subjects is needed.

Key Datasets for analysis: The following datasets are defined for this trial:

- [REDACTED]
- [REDACTED]
- [REDACTED]
- [REDACTED]

Primary efficacy analysis: [REDACTED]

Statistical Methods, cont.:
	
Key secondary efficacy analysis: [REDACTED]
 
Safety analyses: [REDACTED]

Trial Duration:
	
The duration of the double-blind, randomized treatment period will be 12 months. The total duration for each subject entered into the trial is approximately 15-17 months (including the pre-randomization and follow-up periods, and an additional 8 weeks for extension of the screening period in subjects for whom this is necessary).

Table of Contents

Protocol Synopsis	3
Table of Contents	11
List of In-text Tables	16
List of In-text Figures	17
List of Appendices	18
List of Abbreviations and Definitions of Terms	19
1 Introduction	22
1.1 Nonclinical Data	23
1.2 Clinical Data	23

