where $\delta_{i,j}$, as a random effect of change from pre-treatment baseline at visit j for subject i . These $\delta_{i,j}$ s jointly follow a multivariate normal distribution with means being $\delta_{p,j}$ for placebo subjects and $\delta_{T,j}$ for tolvaptan subjects. Their individual variance is assumed to be $\sigma_{\delta_j}^2$. These $\delta_{i,j}$ s are supposed to be correlated; however, their correlations are not utilized for the purpose of sample size calculation in this protocol. In addition, α_i s are assumed iid to have a normal distribution, $\varepsilon_{i,j}$ are assumed iid $N(0, \sigma^2)$, and these random variables are mutually independent. Then, the change from baseline data follows this common MMRM model

$$Y_{i,j} - Y_{i,0} = \delta_{i,j} - \varepsilon_{i,0} + \varepsilon_{i,j} = \zeta_{i,j} + \varepsilon_{i,j} \quad (3)$$

where $\zeta_{i,j} = \delta_{i,j} - \varepsilon_{i,0}$. Note that the variance of $\zeta_{i,j}$ (denoted by $\sigma_{\zeta_j}^2$) is equal to $\sigma_{\delta_j}^2 + \sigma^2$. This model becomes a one-way random effect model if we only consider the post-treatment follow-up visits for a treatment group. Thus, applying a one-way random effect model to the change from pre-treatment baseline to post-treatment follow-up data of placebo and tolvaptan respectively, in subjects who had both follow-up visits and baseline in [REDACTED], σ^2 is estimated as [REDACTED]. Take the average of these two estimates of σ^2 to obtain an estimate of σ^2 as 7.1 to be used in this sample size calculation, which is the σ^2 [REDACTED]. Note that

$$\text{Var}(Y_{i,j} - Y_{i,0}) = \sigma_{\delta_j}^2 + 2\sigma^2 \quad (4)$$

At Month 12, the SD (Standard Deviation) could be assumed as [REDACTED]. Then based on (4), $\sigma_{\delta,j}^2$ at Month 12 is estimated as 28.05 [REDACTED].

With k repeated measurements at pre-treatment baseline and at 12 month post-treatment follow-up in this trial, the baseline intra-subject variance and the follow-up intra-subject variance are reduced from σ^2 to σ^2/k respectively. Thus, the variance of average change from average baseline at Month 12 is $(\sigma_{\delta,12}^2 + \sigma^2/k) + \sigma^2/k$, which is estimated as 31.6 [REDACTED] when k = 4 and 32.8 [REDACTED] when k = 3. Here we have the following table of sample size:

# of Blood draws	1	2	3	4
90% power	1722	1434	1336	1288
85% power	1477	1230	1146	1106
80% power	1286	1070	998	962

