Total Sample Size with $\Delta = 1.07$ and 10% Dropout Rate (Alpha = 0.05)				
# of Blood Draws	1	2	3	4
90% Power	1722	1434	1336	1288
85% Power	1477	1230	1146	1106
80% Power	1286	1070	998	962

From the sample size table, the increase of repeated measurement at baseline and follow-up reduces the sample size significantly initially but quickly loses its effect when k is greater than 3. It seems that 3 repeated measurements may be appropriate in order to avoid patients' burden. Thus, with an assumption of 10% dropout rate in the trial, the total sample size (randomized subjects) would be approximately 1300.

The desire for a small number of blood draws during these periods was emphasized by the trial's Steering Committee who further suggested that measures be taken to minimize the intra-subject variability by standardizing, as much as possible, the timing and conditions by which serum creatinine was assessed (in particular recommending a similar diet, avoiding variation in cooked or uncooked protein intake and exercise pattern be used during these periods). The Steering Committee also suggested that the intra-subject variance during the pre-treatment and post-treatment periods be monitored throughout the trial with a mandatory increase in serum creatinine sample number (ie, from a minimum of 3 to a minimum of 4) or subject numbers if observed variance was greater than that used in the power assumption (assessed using only baseline eGFR data in a power re-estimation procedure). They also favored the possibility that sample numbers, but not the

minimum enrollment, be lowered (ie, to a maximum of 3) if variance was significantly less due to these measures. (See Section 4.2 “Blinded Sample Size Re-estimation”).

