Note that the SD of average change from baseline at Follow-up is 8.00, which is greater than the SD used in the sample size calculation (5.73, equal to the square root of 32.8). However, out of the 11 subjects in the follow-up visit, only one is a completer and the other 10 are early dropouts. Thus, the variance at the follow-up visit may be inflated by the dropout subjects. In addition, for visits with large amount of subjects, say, visits from Month 1 to Month 7, where subject numbers ranged from 60 to more than 200, the

variances of these visits are all less than 6. This raises the possibility that, when we have enough subjects in the follow-up visits so that they are not dominant by early dropouts, the SD of the average change from baseline at follow-up may also be around 6. If this is the case, the trial would be well powered. Even when the SD raised up to 6.5, the trial would still have at least 80% power. Because of this, with the limit of the current data for this blinded sample size re-calculation exercise, no conclusion can be made at this time for the comparison between the observed variances and the variances used in the sample size calculation.

Thus, this blinded sample size re-estimation failed to provide any recommendations to its objectives. The reason for failing the first question is because, when we designed the protocol, it was planned to use eGFR derived from Rate Blank serum creatinine, since this was recommended by our central lab vendor, Covance. However, in a Steering Committee meeting when the trial was under patient enrollment, the Committee Members told us they preferred the Enzymatic serum creatinine. They believed it is the golden standard in deriving eGFR. Because of this, it was decided that eGFR derived from Rate Blank serum creatinine would be used only for patient clinical monitoring, and the eGFR based on Enzymatic serum creatinine obtained from batched analysis on frozen blood samples of all visits would be used in efficacy analyses. This change in clinical operation led to the miss of the first question in this blinded sample size re-estimation exercise.

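### Does the blinded re-estimation memo hide a within-subject variance 1.8 times the planned value?

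*SAP*

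**What the plan says.** Protocol Section 7.1.1 takes the within-subject variance of one eGFR observation "as 7.1 to be used in this sample size calculation". The synopsis puts it as "It is expected that the intra-subject variance is 14.2 and inter-subject variance is 28.05 at Month 12"; 14.2 is 2 × 7.1, baseline plus follow-up. It also states that "the treatment difference in renal function at Month 12 is 1.07 in our sample size calculation", and the calculation is "for a 2-sided alpha set at 0.05 for a power of 90" per cent. With three draws at each end and 10% dropout, the sample size table gives 1336, rounded in the text to about 1300.

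SAP Section 4.1 reports what the Steering Committee suggested, namely "mandatory increase in serum creatinine sample number (ie, from a minimum of 3 to a minimum of 4) or subject numbers if observed variance was" above the planning value. The same sentence specifies that this be judged on baseline eGFR alone. Protocol Section 7.1.2 is milder: the numbers may need adjusting.

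In SAP Appendix 5, Table 2 analyses change from baseline at the follow-up visits: within-subject mean square 12.82 on 15 df, between-subject 189.97 on 9 df. From the 6.7% ratio the memo infers that "we may conclude that the increase of eGFR observations (use of more than one observation) does not reduce the variance of their average much". It then points out that these values come from the rate-blanked assay while efficacy will use the enzymatic one, and finds no grounds to alter the number of draws. Under Question 2 it sets an observed SD of 8.00 against the planned 5.73. It remarks that "the variance at the follow-up visit may be inflated by the dropout subjects" (ten of the eleven subjects were early dropouts) and says no conclusion can be drawn.

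**The concern.** Three things look wrong together. First, the between-subject mean square estimates the within-subject variance plus roughly 2.5 times the between-subject component, so its ratio to the within-subject mean square understates the within-subject share. Second, the re-estimation was meant to compare observed with planned variances. The natural comparison is 12.82 against 7.1, and in the visible text the memo calls the within-subject error small without making it. Third, the between-subject spread that makes 12.82 look small comes from the same follow-up data that Question 2 distrusts.

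If 12.82 were a sound estimate, the stated 90% power would be optimistic, and a reason to add draws or subjects would have been passed over.

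**Working it through.** **The plan's own figure.** Variance of the average change with k draws at each end: 28.05 + 2 × 7.1/k. For k = 3 this is 32.78 (SD 5.73). Per arm: 2 × (1.960 + 1.282)² × 32.78 / 1.07² ≈ 602. The total is 1204 evaluable, and 1204/0.9 ≈ 1338 randomized, against 1336 in the table. At 1300 randomized (585 evaluable per arm) power is 89.2%.

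**The ratio.** 1709.75/9 = 189.97, 192.36/15 = 12.82, and 12.82/189.97 = 6.7%. Nine between-subject df and 25 values mean 10 subjects. (Table 3 lists 11 subjects at Day 7, a small mismatch.) The split of draws is not shown. Assuming seven subjects with 3 values, one with 2 and two with 1, n0 = (25 − 69/25)/9 = 2.47.
- Between-subject component: (189.97 − 12.82)/2.47 ≈ 71.7.
- Within-subject share of one observation: 12.82/(71.7 + 12.82) ≈ 15%.
- Ratio expected under the planned components, with n0 = 2.5 and baseline error included: 7.1/(7.1 + 2.5 × (28.05 + 7.1/3)) ≈ 8.5%.

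A ratio near 7% is therefore about what the plan itself implies, and it does not show that within-subject error is small.

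**Power if 12.82 held.** 12.82/7.1 = 1.81. Applied at both ends with 28.05 kept: 28.05 + 2 × 12.82/3 = 36.60, SD 6.05, power 85.7% at 1300. If it applied to follow-up only, power would be 87.4%. The 95% chi-square interval for the variance on 15 df is 7.0 to 30.7, which just includes 7.1.

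**What produces 12.82.** In Table 3 the largest changes at follow-up Days 7, 14 and 21 are 17.18, 17.18 and 29.72.
- Their mean is 64.08/3 = 21.36, exactly the maximum in the follow-up average row.
- The eGFR maxima 81.95, 81.95 and 94.49 average 86.13, again the maximum in that row.
- All three pairs imply the same baseline: 81.95 − 17.18 = 94.49 − 29.72 = 64.77.

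This is one subject. The subject is in the ANOVA: rebuilding the total sum of squares from the three visit rows (n, mean, SD) gives 1902.9, against 1902.10 in Table 2.

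That subject's within-subject sum of squares is 2 × (17.18 − 21.36)² + (29.72 − 21.36)² = 34.9 + 69.9 = 104.8, or 54% of 192.36. Removing it leaves 87.5 on 13 df, a mean square of 6.73. The variance is then 28.05 + 2 × 6.73/3 = 32.5, and power at 1300 is 89.4%.

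**The memo's sentence on its own data.** With a between-subject component of 71.7, averaging three follow-up draws rather than one changes the variance from 71.7 + 12.82 = 84.5 to 71.7 + 12.82/3 = 76.0, a fall of about 10%. With the planned 28.05 and 12.82 at both ends, the fall from one draw to three would be 32%.

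**The case for a change.** The best case for a change is that the memo's inference is invalid whatever the data show. It calls an error small when the point estimate lies above plan, and it expects the rate-blanked assay to be the less variable one, which makes a high value more notable. Dropping the most extreme subject after the fact also biases the estimate downwards, so 6.73 is no better an estimate than 12.82. Table 3 shows about 340 subjects with a baseline, and SAP Section 4.2 prescribes an analysis of their baseline replicates, which would be far more precise.

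The first part stands: the ratio is misread, and 12.82 is not set beside 7.1 in the visible text. The point about dropping a subject also stands. The 6.73 is a sensitivity check; it shows that about ten subjects cannot separate a variance of 7 from one of 13.

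The rest does not lead to action. The Section 4.1 suggestion rests on baseline data, so a follow-up mean square neither triggers nor masks it. The memo's text before Table 2 is blacked out and may already hold the baseline analysis and the comparison with 7.1, so neither can be called missing. A rerun on the data the memo used would again rest on rate-blanked values, which SAP Section 8.3 says cannot be exchanged with the enzymatic ones used for efficacy.

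**Conclusion.** No change is needed. The memo contains a real slip: 6.7% is not the within-subject share of variance, which is about 15% in these data. The alarming reading of 12.82 does not hold. The estimate rests on about ten subjects, its interval of 7.0 to 30.7 includes 7.1, and a single subject moves it from 6.73 to 12.82. These data neither confirm nor contradict the planned value, so there is no basis for restating power as 86%.

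Even at face value the loss is 89.2 − 85.7 = 3.5 points. The implied SD of 6.05 falls within the range the memo already discusses: it regards an SD around 6 as well powered (86.2% by the same formula) and 6.5 as keeping at least 80% (80.4%).

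Nothing was decided on the strength of the sentence. Three draws were kept because of the assay mismatch, and the memo says the exercise yielded no recommendation. SAP version 6 is dated March 2017 and its Section 10 refers to final enrolment, so adding draws or subjects is no longer a live option. Section 8.3 estimates the variance components for the primary weights from the trial's own data, so the planning value of 7.1 does not enter the result.

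This rests on the Table 3 maxima belonging to one subject, which the matching means and common baseline support. The power figures also assume a between-subject variance of 28.05 and 10% dropout from 1300.

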Note that the SD of average change from baseline at Follow-up is 8.00, which is greater than the SD used in the sample size calculation (5.73, equal to the square root of 32.8). However, out of the 11 subjects in the follow-up visit, only one is a completer and the other 10 are early dropouts. Thus, the variance at the follow-up visit may be inflated by the dropout subjects. In addition, for visits with large amount of subjects, say, visits from Month 1 to Month 7, where subject numbers ranged from 60 to more than 200, the

variances of these visits are all less than 6. This raises the possibility that, when we have enough subjects in the follow-up visits so that they are not dominant by early dropouts, the SD of the average change from baseline at follow-up may also be around 6. If this is the case, the trial would be well powered. Even when the SD raised up to 6.5, the trial would still have at least 80% power. Because of this, with the limit of the current data for this blinded sample size re-calculation exercise, no conclusion can be made at this time for the comparison between the observed variances and the variances used in the sample size calculation.

Thus, this blinded sample size re-estimation failed to provide any recommendations to its objectives. The reason for failing the first question is because, when we designed the protocol, it was planned to use eGFR derived from Rate Blank serum creatinine, since this was recommended by our central lab vendor, Covance. However, in a Steering Committee meeting when the trial was under patient enrollment, the Committee Members told us they preferred the Enzymatic serum creatinine. They believed it is the golden standard in deriving eGFR. Because of this, it was decided that eGFR derived from Rate Blank serum creatinine would be used only for patient clinical monitoring, and the eGFR based on Enzymatic serum creatinine obtained from batched analysis on frozen blood samples of all visits would be used in efficacy analyses. This change in clinical operation led to the miss of the first question in this blinded sample size re-estimation exercise.

The reason for missing of the second objective in this blinded sample size re-estimation exercise is that, when we designed the protocol, we would like to make sure the sample size re-estimation would be done before half of the planned subjects were randomized. Had we specified to conduct the blinded sample size re-estimation at a time when 600 - 700 subjects were randomized to the trial, or when 40 - 50 subjects completed their 12-month post-treatment follow-up, which ever came later, we should not have problem to answer the second question.

